## 9.3.1. Recommended Actions with Sacituzumab Govitecan-hziy for Adverse Events

Recommended dose levels for reduction of sacituzumab govitecan-hziy dose are described below. Sacituzumab govitecan-hziy dose reductions for hematologic toxicities are based on values obtained within 24 hours prior to Day 1 or Day 8 of a given cycle per Investigator discretion and institutional guidelines; recommendations are provided in Table 8. All dose reductions for an individual patient are permanent; and the dose, which has been reduced for toxicity, must not be re-escalated. Up to a maximum of 2 dose reductions will be allowed per patient. If a third dose reduction is required per the modifications below, the patient should discontinue study treatment.

• Starting dose: 10 mg/kg

• First dose reduction: 25% from original dose

Second dose reduction: 50% from original dose

• Third dose reduction: discontinue all study drugs

Note that dose modifications (specifically dose reductions/discontinuations) are recommended for those events considered related to drug (i.e., toxicities) such that decreasing the dose or stopping the drug will lead to improved patient safety. If an event is not thought to be related to study drug by the Investigator, dose reduction/discontinuation is not required since decreasing the dose or stopping the drug would not be expected to alter the risk of the event occurring again; rather, the Investigator should consider if treatment should be delayed until the event recovers to  $\leq$ Grade 1 or baseline before resumption of treatment. Decreased neutrophil, platelet counts or hemoglobin values that occur in isolation (e.g., at nadir) that do not result in a dosing delay, febrile neutropenia, serious adverse event (SAE) or other consequence, do not require dose modification.

If drug-related toxicity requires discontinuation of sacituzumab govitecan-hziy or trilaciclib then the patient must permanently discontinue all study drugs and should complete the Post-Treatment Visit and enter Survival Follow-up.

G1T28-213

Table 8: Recommended Dose Modifications for Sacituzumab Govitecan-hziy

Adverse Event	Occurrence	Dose Modification
Severe Neutropenia		
Grade 4 neutropenia ≥7 days	First	25% dose reduction
OR		and administer
Grade 3 febrile neutropenia (ANC <1000/mm³ and fever		G-CSF
≥38.5°C)	Second	50% dose reduction
OR	Third	Discontinue treatment
At time of scheduled treatment, Grade 3-4 neutropenia		
which delays dosing by 2 or 3 weeks for recovery to		
≤Grade 1		
At time of scheduled treatment, Grade 3-4 neutropenia	First	Discontinue treatment
which delays dosing beyond 3 weeks for recovery to		
≤Grade 1		
Severe Non-Neutropenic Toxicity		
Grade 4 non-hematologic toxicity of any duration	First	25% dose reduction
OR	Second	50% dose reduction
Any Grade 3-4 nausea, vomiting, or diarrhea due to	Third	Discontinue treatment
treatment that is not controlled with antiemetics and		
anti-diarrheal agents		
OR		
Grade 3-4 non-hematologic toxicity persisting >48 hours		
despite optimal medical management		
OR		
At time of scheduled treatment, Grade 3-4 non-neutropenic		
hematologic or non-hematologic toxicity, which delays		
dose by 2 or 3 weeks for recovery to ≤Grade 1		
In the event of Grade 3-4 non-neutropenic hematologic or	First	Discontinue treatment
non-hematologic toxicity, which does not recover to		
≤Grade 1 within 3 weeks		

ANC=absolute neutrophil count; G-CSF=granulocyte colony-stimulating factor

Source: Table recreated from Trodelvy Package Insert, 2021

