# 9.3. Toxicity Management and Dose Modifications

The dose of trilaciclib will not be modified and will remain at 240 mg/m^2 throughout the study. If administration of sacituzumab govitecan-hziy is discontinued, trilaciclib will also be discontinued.

The dose of sacituzumab govitecan-hziy can be reduced, when necessary, as described below. The recommended dose modification procedures for hematologic and non-hematologic toxicities are described in Table 8. If a subsequent cycle is delayed for toxicity, the patient should still complete the clinical laboratory assessments on the scheduled Day 1 (entered as an Unscheduled assessment in electronic data capture [EDC]) as well as on the actual first dosing day of that cycle. If the delay is secondary to hematologic toxicity, weekly repeat hematology assessments should continue until the finding meets criteria for resumption of dosing.

Treatment with sacituzumab govitecan-hziy will be permanently discontinued for a patient in the event of any Grade 4 infusion reactions which occur after pre-medication with antihistamines, H2 blockers, and steroids.

Recommendation for management of trilaciclib AESIs are provided in Table 9. Recommendations for hepatobiliary toxicity management are in Section 9.3.3.

For dose delays due to toxicity, the patient should be followed (at least) weekly, including CBCs if the AE is hematologic, to monitor the toxicity until treatment criteria are met or until they discontinue treatment. A 3-week delay from the scheduled dose of sacituzumab govitecan-hziy is permitted for toxicity and/or administrative reasons. As examples, if at the scheduled Cycle X Day 1 visit (e.g., Cycle 2 Day 1) a dose delay is needed for toxicity reasons, a delay up to 3 weeks from Cycle X Day 1 for sacituzumab govitecan-hziy is permitted; if at the scheduled Cycle X Day 8 visit (e.g., Cycle 1 Day 8) a dose delay is needed for toxicity reasons, a delay up to 3 weeks from Cycle X Day 1 for sacituzumab govitecan-hziy is permitted. Dosing delays >3 weeks from the scheduled dose of sacituzumab govitecan-hziy may be permitted on a case by-case basis with the documented approval of the Investigator and Medical Monitor.

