7.3. Study Drug Modifications

Study drug modifications will be summarized at the final analysis.

There are three types of study drug modification: dose reduction, cycle delay, and infusion interruption. The number of protocol-permitted dose reductions for each study drug are summarized in Table 5.

Table 5Protocol Permitted Dose Reduction by Study Drug

Study Drug	Number of Dose Reductions Allowed			
Trilaciclib/placebo	0			
Sacituzumab govitecan-hziy	2			

Study drug modifications will be summarized in each of the following categories: chemotherapy dose reduction, treatment cycle delay, and infusion interruption. The number and percentage of patients who had any chemotherapy dose reduction, any cycle delay, cycle delay due to hematological toxicity, or any infusion interruption will be summarized.

In addition, more detailed summaries outlined below will be provided.

Dose reduction for Sacituzumab govitecan-hziv. For Sacituzumab govitecan-hziy, the number and percentage of patients who had at least one dose reduction will be summarized. In addition, the number and percentage of patients will be summarized in the following mutually exclusive categories: "Not Applicable (cycle 1 treatment only)", 0, 1, or 2 reductions for the drug. The primary reason for dose reduction will be summarized.

Cycle delay. Information regarding whether a cycle was delayed was collected in the eCRF for each cycle. The number of cycles that have been delayed will be summarized as a continuous variable. In addition, the number and percentage of patients in each of the following mutually exclusive categories will be summarized: "Not Applicable (cycle 1 treatment only)", 0, 1, 2, …, maximum number of delays.

The reasons for cycle delay collected in eCRF are as follows:

- Low neutrophil count
- Low platelet count
- Both low neutrophil count and low platelet count
- Other hematologic toxicity
- Non-hematologic toxicity
- Other

Patients with reasons entered in the "Other" category will be further classified based on medical review of comments collected on the eCRFs into finer categories as appropriate.

Infusion interruption. Infusion interruption was captured in the eCRF for each study drug with the reasons. Any infusion interruption is defined as infusion interruption of any study drug.

The number of any and trilaciclib infusion interruptions will be summarized descriptively and categorically.

Corresponding data listings will be provided for dose modifications.

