8.1.4.3. Dose Modifications

Occurrence and Number of SG Dose Reduction

The occurrence of a dose reduction for a patient is defined as having at least one dose reduction of SG in a cycle. Occurrence of SG dose reduction is a binary random variable (Yes or No).

Number of SG dose reductions for a patient is defined as the total counts of SG dose reductions. In addition, SG that was permanently discontinued due to toxicity will be also counted as a dose reduction event. The value of 0 will be assigned to those patients who did not have any SG dose reductions. Number of SG dose reductions is a counting random variable and the summary statistics for this variable is event rate per 100 cycles.

Occurrence and Number of Cycle Delays Due to Hematologic Toxicity

Occurrence of cycle delays and the associated reason is collected in detail in the eCRF with the following mutually exclusive categories: Low neutrophil count, Low platelet count, Both low neutrophil count and low platelet count, Other hematologic toxicity, Non-hematologic toxicity, or Other. A cycle that was marked as delayed with the reason of Low neutrophil count, Low platelet count, Both low neutrophil count and low platelet count, or Other hematologic toxicity is considered a delay due to hematologic toxicity.

Occurrence of cycle delays due to hematologic toxicity for a patient is defined as having at least one cycle delay due to hematologic toxicity and is a binary random variable (Yes or No). The number of cycle delays due to hematologic toxicity for a patient is defined as the total number of cycles that were delayed due to such reason for the patient during the treatment period. For patients who did not have any cycle delays due to hematologic toxicity, the value of 0 will be assigned. Number of cycle delays due to toxicity is a counting random variable and the summary statistics for this variable is event rate per 100 cycles.

The analysis of myeloprotection endpoints will be based on the FAS population.

G1 Therapeutics

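### SAP 7.3 treats SG dose reduction as not applicable to every patient treated in Cycle 1 only, although a reduction can be made at Cycle 1 Day 8, so the breakdown by number of reductions misclassifies these patients

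*Protocol*

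**What the plan says.** SAP 7.3 plans two displays of SG dose reduction, one after the other. The first has no Cycle 1 exclusion: "For Sacituzumab govitecan-hziy, the number and percentage of patients who had at least one dose reduction will be summarized". The second divides patients into mutually exclusive categories. One is labelled "Not Applicable (cycle 1 treatment only" (closing bracket omitted here), and the others are 0, 1 and 2 reductions. The same Not Applicable label is used again in the cycle-delay paragraph of that section.

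Protocol 9.3.1 says that SG "dose reductions for hematologic toxicities are based on values obtained within 24 hours prior to Day 1 or Day 8 of a given cycle". Protocol 9.3 names Cycle 1 Day 8 as a visit at which toxicity can change dosing; its example is a delay: "if at the scheduled Cycle X Day 8 visit (e.g., Cycle 1 Day 8) a dose delay is needed for toxicity reasons". Protocol Table 8 lists the reduction triggers without restricting them by cycle, among them "Grade 4 non-hematologic toxicity of any duration".

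SAP 8.1.4.3 defines the occurrence endpoint as "having at least one dose reduction of SG in a cycle", again with no exception for Cycle 1. Protocol 12.4.5 asks for patients with any SG reduction and has no Not Applicable class. SAP Section 10, which lists the changes from the protocol, does not mention one.

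**The concern.** A Not Applicable row is sound only if its members could not have had the event. Each 21-day cycle has two SG doses, so a patient who received both Cycle 1 doses had one opportunity for a reduced dose. The label fits cycle delay, because Cycle 1 has no preceding cycle from which it could be delayed. It does not fit dose reduction.

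SG dose reduction is a listed secondary safety endpoint and also appears among the myeloprotection endpoints in SAP Table 7. Patients who stop within Cycle 1 may include those with the poorest early tolerability. A breakdown that sets them aside, next to a row that includes them, gives the reader two figures that need not agree and no explanation of the difference.

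**Working it through.** The plan states no figure on this point, so there is none to reproduce. The check compares the passages and then does simple arithmetic on the final sample size.

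**Step 1: the earliest possible reduction.** Cycle 1 Day 1 is given at the starting dose. Protocol 9.3.1 allows hematologic reductions at Day 1 or Day 8 of a cycle, and Table 8 does not restrict the non-hematologic triggers by cycle. The first dose that can be reduced is therefore Cycle 1 Day 8. The protocol does not say this in so many words; it follows from the two provisions together.

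**Step 2: whether a trigger can occur in time.** Grade 4 non-hematologic toxicity of any duration, uncontrolled Grade 3-4 nausea, vomiting or diarrhea, and Grade 3-4 non-hematologic toxicity lasting more than 48 hours can all arise between Day 1 and Day 8. A Day 8 dose postponed for toxicity is a further, narrower route.

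**Step 3: where the SAP 7.3 rules place each patient.**

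| Patient | Any-reduction row | Breakdown as written | Actual number |
|---|---|---|---|
| Cycle 1 only, Day 8 dose reduced | counted | Not Applicable and 1 both fit | 1 |
| Cycle 1 only, both doses in full | not counted | Not Applicable | 0 |
| Cycle 1 only, Day 1 dose alone | not counted | Not Applicable | no opportunity |

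Only the third patient belongs in Not Applicable. The first fits two categories that are declared mutually exclusive, and SAP 7.3 gives no rule for choosing between them.

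**Step 4: the size of the gap.** SAP 1.3 gives a final sample size of 30. Assume that all 30 were dosed and so form the safety population. Let r be the patients first reduced in Cycle 2 or later, m the Cycle-1-only patients, and j those of the m reduced at Day 8. Take the label literally, so that all m go to Not Applicable.

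- Any-reduction row = (r + j)/30
- Rows 1 and 2 together = r/30
- Gap = j/30 = 3.3 percentage points per patient

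The documents give none of r, m or j. As an illustration only, take r = 5 and m = 3, with all three having received a Day 8 dose:

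| j | Any-reduction row | Rows 1+2 as written | Gap (points) | Row 0 as written | Row 0 corrected |
|---|---|---|---|---|---|
| 0 | 5/30 (16.7%) | 5/30 (16.7%) | 0.0 | 22 | 25 |
| 1 | 6/30 (20.0%) | 5/30 (16.7%) | 3.3 | 22 | 24 |
| 2 | 7/30 (23.3%) | 5/30 (16.7%) | 6.7 | 22 | 23 |
| 3 | 8/30 (26.7%) | 5/30 (16.7%) | 10.0 | 22 | 22 |

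Row 0 as written is 30 − 3 − 5 = 22. Corrected, it is 22 + (3 − j). With the corrected rule, rows 1 and 2 total 5 + j and the gap is zero for every j.

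**Step 5: agreement with SAP 8.1.4.3.** That section also counts permanent SG discontinuation for toxicity as a reduction event in the number of reductions. SAP 7.3 does not mention discontinuation, and its categories stop at 2, whereas Protocol 9.3.1 treats a third reduction as discontinuation. So even with the categories corrected, the 7.3 breakdown and the 8.1.4.3 count can differ by definition.

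**The case against.** A reader might infer that these reductions vanish from the report, or that the secondary endpoint is biased. The documents do not support either reading. The any-reduction row comes immediately before the breakdown and has no Cycle 1 exclusion. SAP 7.3 also summarizes reasons for reduction and provides listings, and the SAP 8.1.4.3 endpoints count the events. Protocol 12.4.5 asks only for the any-reduction figure and the reasons, and both are delivered. The breakdown is an additional display.

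The route is also narrow. The patient must meet a trigger after one dose, receive a reduced Day 8 dose and never start Cycle 2. Hematologic triggers are unlikely to act that early: Grade 4 neutropenia lasting at least 7 days can hardly be established by an on-time Day 8, Protocol 9.2 requires an ANC of at least 1.0 × 10⁹/L for the Day 8 dose, and Protocol 4.2.3 cites a median of 21 days to first Grade 3 or higher neutropenia. Finally, the table shells are separate documents and may settle which category takes precedence.

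Most of this stands, and it keeps the point small. It does not remove it. The non-hematologic triggers remain possible before Day 8. Patients given both Cycle 1 doses in full are kept out of row 0 whether or not anyone was reduced. A shell that has not been seen cannot be relied on to correct a category that the SAP itself states.

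**Conclusion.** The point holds as a classification error in one descriptive table. The four categories in SAP 7.3 overlap for a Cycle-1-only patient reduced at Day 8, and they wrongly exclude from row 0 a Cycle-1-only patient who received both doses in full. Each patient of the first kind, if placed in Not Applicable as the label directs, makes rows 1 and 2 fall short of the any-reduction row by 3.3 points out of 30. With no such patient the shortfall is zero and only row 0 is affected.

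This rests on reading Cycle 1 Day 8 as a visit where a reduction may be made, which is a sound inference rather than an explicit statement, and on a safety population of 30. The patient counts in the illustration are assumptions. Severity is low: no efficacy analysis, including PFS, changes.

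**What to change.** In SAP 7.3, for dose reduction only:

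- Limit Not Applicable to patients who received no SG dose after Cycle 1 Day 1.
- Classify all other patients, including those treated in Cycle 1 only, by their observed number of reductions: 0, 1 or 2.
- Add a footnote that this display does not count permanent SG discontinuation for toxicity as a reduction, whereas the SAP 8.1.4.3 count does, so that the two can be reconciled.

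Leave the present label in place for cycle delay. The cost is one line of SAP and table-shell wording plus the footnote. No new data are needed, because the dose at each visit is already collected.

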# 9.3.2. Recommended Actions with Trilaciclib for Adverse Events of Special Interest (AESI)

Suggested actions to be taken with trilaciclib following AESI are provided in Table 9.

G1T28-213

Table 9: Recommended Actions with Trilaciclib Following AESIs

AESI	Severity	Recommended Action
Injection site reactions including phlebitis and thrombophlebitis	Grade 1: Tenderness with or without symptoms (e.g. warmth, erythema, itching)	Interrupt or slow infusion of trilaciclib. If 0.9% normal saline is being used as a diluent/flush, consider changing to 5% dextrose as appropriate for subsequent infusions.
	Grade 2: Pain; lipodystrophy; edema; phlebitis	Interrupt infusion of trilaciclib. If pain not severe, follow instructions for Grade 1. Otherwise, stop infusion in extremity and rotate site of infusion to site in alternative extremity. If 0.9% normal saline is being used as a diluent/flush, consider changing to 5% dextrose as appropriate for subsequent infusions. Central access may also be considered.
	Grade 3: Ulceration or necrosis; severe tissue damage; operative intervention indicated.  Grade 4: Life threatening consequences; urgent interventions indicated.	Stop infusion and permanently discontinue trilaciclib.
	Grade 2: Moderate; minimal, local or noninvasive intervention indicated; limiting ADL	Stop infusion and hold trilaciclib until recovery to Grade ≤1 or baseline, then consider resuming trilaciclib. If Grade 2 recurs, permanently discontinue trilaciclib.
Acute drug hypersensitivity reactions	Grade 3: Severe or medically significant but not immediately life-threatening; hospitalization or prolongation of hospitalization indicated; disabling; limiting self-care ADL OR Grade 4: Life-threatening consequences; urgent intervention indicated	Permanently discontinue trilaciclib.
ILD/pneumonitis	Grade 2 (symptomatic)	Hold trilaciclib until recovery to Grade ≤1 or baseline, then consider resuming trilaciclib.  If Grade 2 recurs, permanently discontinue trilaciclib.

AESI	Severity	Recommended Action
	Grades 3: Severe symptoms; limiting self-care ADL; oxygen indicated	
	OR Grade 4: Life-threatening respiratory compromise; urgent intervention indicated (e.g., tracheotomy or intubation)	Permanently discontinue trilaciclib.

AESI=adverse event of special interest; ADL=activities of daily living; ILD=interstitial lung disease

## 9.3.3. Hy's Law Management

Abnormal values in AST and/or ALT concurrent with abnormal elevations in total bilirubin that meet the criteria outlined below in the absence of other causes of liver injury are considered potential cases of drug-induced liver injury (potential Hy's Law cases) and should always be considered important medical events.

The threshold of laboratory abnormalities for a potential case of drug-induced liver injury depends on the patient's individual baseline values and underlying conditions. Patients who present with the following laboratory abnormalities should be evaluated further to determine the etiology of the abnormal laboratory values:

- Baseline AST or ALT and total bilirubin values are within the normal range and
  the patient subsequently presents with AST or ALT ≥3 × ULN concurrent with a
  total bilirubin ≥2 × ULN with no evidence of hemolysis and an alkaline
  phosphatase ≤2 × ULN or not available.
- Preexisting ALT OR AST OR total bilirubin values above the upper limit of normal, and the patient subsequently presents with:
  - AST or ALT  $\geq$ 2 times the baseline values and  $\geq$ 3 × ULN, or  $\geq$ 8 × ULN (whichever is smaller)
  - Concurrent with total bilirubin increased by one time the baseline value OR >3 × ULN (whichever is smaller).

The patient should return to the investigational site and be evaluated as soon as possible, preferably within 48 hours from awareness of the abnormal results. This evaluation should include laboratory tests, detailed history, and physical assessment. In addition to repeating AST and ALT, laboratory tests should include albumin, creatine kinase, total bilirubin, direct and indirect bilirubin, gamma-glutamyl transferase, prothrombin time/International Normalized Ratio (INR), and alkaline phosphatase. A detailed history, including relevant information, such as review of ethanol, acetaminophen, recreational drug and supplement consumption, family history, occupational exposure, sexual history, travel history, history of contact with a jaundiced patient, surgery, blood transfusion, history of liver or allergic disease, and work exposure, should be collected. Further testing for acute hepatitis A, B, or C infection and liver imaging (e.g., biliary tract) may be warranted.

G1T28-213

All cases confirmed on repeat testing as meeting the laboratory criteria defined above, with no other cause for liver function test (LFT) abnormalities identified at the time should be considered potential Hy's Law cases irrespective of availability of all the results of the investigations performed to determine etiology of the abnormal LFTs. Such potential Hy's Law cases should be promptly reported as SAEs via the EDC.

# 9.4. Supportive Care Interventions

## 9.4.1. Colony Stimulating Factor Usage

Use of prophylactic colony stimulating factors (e.g., G-CSF; granulocyte-macrophage colony-stimulating factor [GM-CSF]) during Cycle 1 (i.e., prior to the actual Cycle 2 Day 1 dosing visit) is not allowed. In subsequent cycles (Cycle 2 and beyond), prophylactic colony-stimulating factors are allowed as outlined in Table 8, which are based on the ASCO guidelines for neutropenia (Smith, 2015) and package inserts. If in any cycle (including Cycle 1), a patient experiences severe neutropenia (Grade 4) or febrile neutropenia and is at high risk for infection-associated complications, or has prognostic factors that are predictive of poor clinical outcomes (Table 10), G-CSF/GM-CSF may be used to treat the severe neutropenia or febrile neutropenia event per ASCO guidelines and package inserts.

Short-acting G-CSF products (i.e., Neupogen or biosimilars) may be administered starting 24 to 48 hours after sacituzumab govitecan-hziy and must be stopped 48 hours prior to study drug administration in the next cycle. Similarly, Neulasta (or biosimilars) or other long half-life G-CSF products (e.g., macapegfilgrastim) may be administered 24 to 48 hours after sacituzumab govitecan-hziy but due to its prolonged half-life should not be repeated within that cycle.

Table 10: Patient Risk Factors for Poor Clinical Outcomes Resulting from Febrile Neutropenia or Infection

Risk Factor
Sepsis syndrome
Age >65 years
Profound neutropenia (absolute neutrophil count <0.1 × 10  /L)
Neutropenia expected to last >10 days
Pneumonia
Invasive fungal infection
Other clinically documented infections
Hospitalization at time of fever
Prior episode of febrile neutropenia

ASCO=American Society of Clinical Oncology

Source: Table recreated from Table 2 of the ASCO guidelines (Smith, 2015; Smith, 2006).

